**INTRODUCTION**

An ageing population, increased activity level, bone fragility and co-morbidities are contributing to the increasing incidence of proximal femoral fractures (PFF).(1) The incidence of hip fracture is predicted to increase to 101,000 by 2020. Falls in the elderly osteoporotic population resulting in hip fracture is the commonest reason for admission to the orthopedic ward. (2) Multi-disciplinary care for the hip fracture patient has reduced one month mortality to 8.2% in recent years but significant morbidity still exists.(3) Analgesia is a key component in the pre-hospital, preoperative and post-operative time periods for the hip fracture patient. Opioids are often required to provide adequate analgesia but can cause nausea, constipation, and confusion (delirium) in the older patient.(4)

**BACKGROUND**

The fascia-iliaca compartment block (FICB) is a relatively new component of the hip fracture analgesia armamentarium. The National Institute of Health and Care Excellence (NICE) recommends the use of simple oral analgesia including opioids, with fascia-iliac blocks used as an adjunct.(5) FICB provided superior analgesia to intramuscular morphine in a randomized controlled trial of 48 hip fracture patients.(6) The analgesic effects were significant both at rest and 15 degree flexion of the hip. In a different study, 24/30 patients who received a FIB were able to assume a semi-recumbent position pre-operatively due to improved hip flexion which provided comfort whilst waiting for surgical intervention.(7) FICB significantly reduced the incidence of delirium in intermediate risk patients.(8) FICB administered in the emergency department by an emergency physician provided significant decrease in pain from 15 minutes - 8 hours post block when compared to standard parenteral medications. Post block analgesic requirements for patients in the FIB group were minimal.(9)

**SIGNIFICANCE**

Ketamine is a noncompetitive antagonist of the N-methyl-D aspartate receptor (NMDAR). It is used for premedication, sedation, induction, and maintenance of general anesthesia.(10) Central, regional, and local anesthetic and analgesic properties have

been reported for ketamine. Intravenous (IV) administration of low-dose ketamine decreases postoperative opioid use and improves analgesia.(11) The addition of ketamine to epidural lidocaine or bupivacaine increases the duration of regional anesthesia and postoperative analgesia.(12) It has been seen that peri-incisional use of 0.3-0.5% ketamine combined with local anesthetic in surgical wounds enhances analgesia by a peripheral mechanism.(13)

Several studies have been performed to evaluate the effect of added ketamine to local anesthetics for nerve block and regional anesthesia. Ketamine did not enhance the onset time and duration of sensory and motor blockade when added to ropivacaine for the interscalene brachial plexus block.(14) Addition of ketamine to ropivacaine infusion via the femoral nerve catheter after repairing an anterior cruciate ligament (ACL) injury/tear could not improve postoperative pain control.(16). However, addition of ketamine to lidocaine for supraclavicular brachial plexus block resulted in greater pain relief and longer time to first request for analgesia. (17)

We are conducting this study to evaluate the effect of ketamine added to bupivacaine at the onset on the duration of sensory and motor block in ultrasound –guided fascia iliaca compartment block for patients presenting to the ED with hip or femur fractures

### **HYPOTHESIS**

1. The administration of ketamine as an adjunct to bupivacaine for ultrasound guided fascia –iliaca nerve block will result in greater and longer lasting analgesia, longer lasting motor and sensory block, and overall less requirements for an opioid rescue analgesia.

### **STUDY DESIGN**

**Subjects:** Patients aged 18 years and older with isolated hip or femur fracture confirmed on x-ray.

### **Eligibility:**

Patients aged 18 years and older with isolated hip or femur fracture confirmed on x-ray.

#### Exclusion Criteria

- Polytrauma
- Unstable vitals signs
- Allergy to Bupivacaine or Ketamine
- Inability to give consent
- Altered mental status
- Known end stage renal disease or hepatic dysfunction
- Received > 2 doses of Morphine in ER prior to regional nerve block
- Patients with failed nerve block (30 minute onset)
- $\geq 100\text{kg}$

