#### **Design:**

A randomized double-blind prospective superiority trial.

- Each patient will receive Morphine for analgesia prior to regional nerve block.
  - Patients < 65 years will receive Morphine 0.1 mg/kg every four hours as needed for 2 doses
  - Patients > 65 years will receive Morphine 0.05 mg/kg every four hours as needed for 2 doses
- **Treatment group:** will receive an ultrasound guided regional nerve block with Bupivacaine (0.5% or 5 mg/ml) 2.5 mg/kg (max dose 175 kg) + Ketamine (50 mg/ml) 2 mg/kg. Each patient will be given a volume of 40 mL - this will be a mixture of Bupivacaine, Ketamine and 0.9% NS to make up the full 40 ml.
- **Control group:** will receive an ultrasound guided regional nerve block with Bupivacaine 0.5% only. Each patient will be given a volume of 40 ml - this will be a mixture of Bupivacaine and 0.9% NS to make up the full volume of 40 mL
- The patients will be followed with respect to accrual time, follow up time, and total time of the block as well as a need for rescue analgesia as follows: every 15 minutes for the first hour; every 30 minutes for the next hour; every 1 hour for next 4 hours; every 4 hours for next 18 hours with end point of 24 hours or up until they are taken to surgery, whichever comes first.
- **Evaluation of the sensory blocks:** will be performed every 5 minutes after administration of the local anesthetic. The sensory block will be quantified as: 0 = Anesthesia (no sensation), 1 = Analgesia (decreased [dull] sensation), and 2 = no block (normal sensation), by using the pinprick test and comparing with the contralateral limb. The time elapsed from the injection to the onset of analgesia in the central sensory region of femoral nerve block will be taken as time of onset of the sensory block.
- **Rescue Analgesia:** If pain is not relieved and the participant requires rescue analgesia a weight-based dose of Morphine will be given at 0.1 mg/kg. In addition, an antidote (lipid emulsion) that will be given to patients who need it when they develop severe side effects.

**Data Collection:** Patient demographic, clinical and injury information, pain score, onset of motor and sensory block, rescue analgesia and side effects will be collected by using a data collection form by trained research assistant and associates.

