**Sample Size:**

A sample size of 110 patients (55 per group) will be needed to detect a 20 % difference in time to first rescue analgesia with  $\alpha = 0.05$  and SD of 2.5. We would recruit 120 patients (60 in each group) to account for any missing data and loss to follow-up.

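### The eligibility rules admit adults from age 18 and do not exclude pregnancy, so a patient known to be pregnant could be randomised to trial-only ketamine in the block (minor, cheap to fix)

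*Combined protocol and SAP*

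**What the plan says.** Study Design and Eligibility give the same entry rule: "Patients aged 18 years and older with isolated hip or femur fracture confirmed on x-ray". There is no upper age limit and no restriction by sex or childbearing potential. The Design section expects some patients who are not elderly, since it sets them a separate morphine dose: "Patients < 65 years will receive Morphine 0.1 mg/kg every four hours as needed for 2 doses".

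The Exclusion Criteria contain nine items. One concerns the study drugs by name: "Allergy to Bupivacaine or Ketamine". The other eight deal with multiple injuries, unstable vital signs, inability to consent, altered mental status, kidney or liver disease, more than two earlier morphine doses, a failed block, and body weight of 100 kg or more.

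The Design section describes "A randomized double-blind prospective superiority trial". The treatment group's block contains bupivacaine plus "Ketamine (50 mg/ml) 2 mg/kg", made up with saline. The control group's block contains bupivacaine and saline only.

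The Background reports a national recommendation for simple analgesia "with fascia-iliac blocks used as an adjunct". The Significance section states the research question: "We are conducting this study to evaluate the effect of ketamine added to bupivacaine".

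**The concern.** An exclusion list says who must not receive the experimental exposure. This one covers drug allergy and organ disease but is silent on pregnancy, although entry starts at 18 and femur fractures are included. Routine testing in the emergency department would not close the gap, because under the written criteria a positive result excludes nobody.

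What is at stake is participant protection. A pregnant patient who consents could be given a drug that she would not receive in the block outside the trial, by blinded assignment, without the protocol having said that this was intended or why. The estimate of treatment effect is not at stake.

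**Working it through.** The plan states no figure on this point, so the check is a reading of the text with two small sums.

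1. **Who can enter.** Study Design and Eligibility require age 18 or over and an isolated, x-ray-confirmed hip or femur fracture. Neither condition removes a pregnant patient.

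2. **Whether any exclusion removes her.**
   - Multiple injuries, unstable vital signs, inability to consent and altered mental status do not apply to a stable, oriented patient with a single fracture.
   - Drug allergy, kidney or liver disease, earlier morphine doses and weight are unrelated to pregnancy as such.
   - Failed block at 30 minutes can be judged only after the block has been given, so it cannot prevent exposure.
   - Result: 9 exclusions, 0 that address pregnancy.

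3. **Whether another section does.** The rest of the supplied text, from the Introduction to Expected Outcomes, does not mention pregnancy, pregnancy testing, breastfeeding, contraception or childbearing potential.

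4. **Which exposure the trial creates.** The Background presents the block as a recommended adjunct, and bupivacaine is in both arms. Ketamine is the planned difference between the arms and is given only by random assignment. The dose is 2 mg/kg × weight. At an illustrative 70 kg this is 2 × 70 = 140 mg. At the weight limit (below 100 kg) it is just under 2 × 100 = 200 mg.

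5. **What added benefit the plan itself expects.** For nerve blocks, the Significance section cites two ropivacaine settings (interscalene block and femoral catheter) without improvement, and one lidocaine setting (supraclavicular block) with better and longer relief. It also reports favourable results by other routes: intravenous, epidural and at the incision. For an addition to a nerve block, the cited evidence is mixed.

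6. **What happens to the statistics.** Sample Size says "We would recruit 120 patients (60 in each group", to cover a requirement of 110. An exclusion applied before randomisation removes patients before they count towards the 120. Both targets, the significance level and the comparison of arms therefore stay as they are.

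**The case against.** The strongest reply has five parts.

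- **No harm is shown.** The documents name no maternal or fetal harm from a single ketamine dose in a block, and the Significance section describes ketamine as an established anaesthetic drug without a pregnancy caution. This stands. A reader might infer that the plan exposes patients to a demonstrated fetal risk, but the text does not support that. The point rests on narrower ground: a trial-only exposure, uncertain added benefit, and no stated decision to include pregnant patients.

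- **It may never happen.** The Introduction describes falls in an older, osteoporotic population. The under-65 morphine dose shows that some younger adults are expected, but not that any will be of childbearing age. This stands too, and it limits the severity. A reader might take the 60/120 = 50% chance of assignment to ketamine as a measure of risk. It only restates equal allocation for someone already enrolled. The documents do not say how many pregnant patients would be enrolled, and the number may be zero.

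- **Consent pages were removed from the supplied text.** They may carry a warning, so it cannot be said that the trial's full materials ignore pregnancy. A warning is not an eligibility rule, however, and the exclusion list is present with no sign of redaction.

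- **Testing has a cost.** A study-mandated test needs a definition of childbearing potential and adds a step before the block for patients in pain. This is a fair objection to requiring a test. It is no objection to excluding pregnancy that is already known.

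- **It is a design preference with no effect on inference.** The second half is correct. The first is not enough: the added line would change who may be dosed, and the plan gives no reason for leaving it out.

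**Conclusion.** The point holds as a minor participant-safety improvement. Followed exactly, the eligibility rules allow a patient known to be pregnant to be randomised to ketamine 2 mg/kg in the block.

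The number affected is probably very small and may be zero. Sample size, error rates and the validity of the between-group comparison are unaffected, and a reader should not infer a weakness in the trial's evidence from this gap. Nor do the documents support a finding that pregnancy testing must be made compulsory.

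The conclusion rests on two assumptions: that the exclusion list as supplied is complete, and that the sponsor did not mean to include pregnant patients. If inclusion was intended, the protocol should say so and give the reason.

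**What to change.** Add one line to the Exclusion Criteria, assessed before randomisation:

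*Known pregnancy, including a positive pregnancy test obtained in usual ED care before randomisation.*

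The criterion uses information already available to the treating team, so it adds no study procedure and does not delay the block. The cost is one line of protocol text and a negligible loss of eligible patients. The sample size and analysis do not change.

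The sponsor may choose to mandate a test in patients of childbearing potential. It would then need to define that group and accept a small extra step before the block. This is optional.

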#### **Design:**

A randomized double-blind prospective superiority trial.

- Each patient will receive Morphine for analgesia prior to regional nerve block.
  - Patients < 65 years will receive Morphine 0.1 mg/kg every four hours as needed for 2 doses
  - Patients > 65 years will receive Morphine 0.05 mg/kg every four hours as needed for 2 doses
- **Treatment group:** will receive an ultrasound guided regional nerve block with Bupivacaine (0.5% or 5 mg/ml) 2.5 mg/kg (max dose 175 kg) + Ketamine (50 mg/ml) 2 mg/kg. Each patient will be given a volume of 40 mL - this will be a mixture of Bupivacaine, Ketamine and 0.9% NS to make up the full 40 ml.
- **Control group:** will receive an ultrasound guided regional nerve block with Bupivacaine 0.5% only. Each patient will be given a volume of 40 ml - this will be a mixture of Bupivacaine and 0.9% NS to make up the full volume of 40 mL
- The patients will be followed with respect to accrual time, follow up time, and total time of the block as well as a need for rescue analgesia as follows: every 15 minutes for the first hour; every 30 minutes for the next hour; every 1 hour for next 4 hours; every 4 hours for next 18 hours with end point of 24 hours or up until they are taken to surgery, whichever comes first.
- **Evaluation of the sensory blocks:** will be performed every 5 minutes after administration of the local anesthetic. The sensory block will be quantified as: 0 = Anesthesia (no sensation), 1 = Analgesia (decreased [dull] sensation), and 2 = no block (normal sensation), by using the pinprick test and comparing with the contralateral limb. The time elapsed from the injection to the onset of analgesia in the central sensory region of femoral nerve block will be taken as time of onset of the sensory block.
- **Rescue Analgesia:** If pain is not relieved and the participant requires rescue analgesia a weight-based dose of Morphine will be given at 0.1 mg/kg. In addition, an antidote (lipid emulsion) that will be given to patients who need it when they develop severe side effects.

**Data Collection:** Patient demographic, clinical and injury information, pain score, onset of motor and sensory block, rescue analgesia and side effects will be collected by using a data collection form by trained research assistant and associates.

**Data Analysis:** Statistical Analyses will include frequency distributions, t-test and chi-square for comparison between and within the groups and Cox Linear Regression Analysis.  $P < .05$  will denote statistical significance. Statistical analyses will be conducted via SPSS version 24. [name] or equivalent will perform the statistical analyses.

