**Expected Outcomes:**

Primary Outcome: time to first rescue analgesia post-regional nerve blockade in each group

Secondary Outcomes:

- Change in pain score as measured by Visual Analog Scale: Patient to be approached at the following intervals: every 15 minutes for the first hour; every 30 minutes for the next hour; every 1 hour for next 4 hours; every 4 hours for next 18 hours with end point of 24 hours or up until they are taken to surgery, whichever comes first.

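### Pre-block morphine varies in dose and timing, and the plan neither lists it for recording nor adjusts the primary analysis for it: a question of precision and chance imbalance, not of bias

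*Combined protocol and SAP*

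**What the plan says.** The Design section of the combined protocol and SAP states: "Each patient will receive Morphine for analgesia prior to regional nerve block". Two lines follow, one per age band: "Patients < 65 years will receive Morphine 0.1 mg/kg every four hours as needed for 2 doses" and "Patients > 65 years will receive Morphine 0.05 mg/kg every four hours as needed for 2 doses".

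The only limit on earlier opioid is under Exclusion Criteria: "Received > 2 doses of Morphine in ER prior to regional nerve block". Two doses is also the most that Design allows, so this rule removes none of the variation that Design permits.

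Expected Outcomes defines the primary outcome as "time to first rescue analgesia post-regional nerve blockade in each group". The rescue drug is again morphine: a participant who "requires rescue analgesia a weight-based dose of Morphine will be given at 0.1 mg/kg".

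Data Collection lists rescue use, pain scores, block onset and side effects, together with general clinical information. It does not name the number, amount or time of pre-block doses. Data Analysis lists t-tests, chi-square tests and a Cox regression without naming covariates, and no stratification of the randomisation is stated.

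**The concern.** The drug given before the clock starts is the same drug whose first use stops it. A patient blocked soon after a second dose may still have opioid cover when the block begins to fade. A patient blocked about four hours after a single dose at the lower rate may have none. Both are eligible, and the plan treats their times as equivalent.

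Time to first rescue could then reflect the wearing-off of earlier morphine as well as the duration of the block. In a trial of 55 to 60 per arm, that could add variance unrelated to ketamine. It could also let a chance difference between arms in last-dose timing move the estimate. If dose and time are not recorded, neither effect can be examined afterwards.

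**Working it through.** **Inputs.** From Design: 0.1 and 0.05 mg/kg, up to two doses, four hours apart. From Sample Size: 55 per group, SD 2.5, alpha 0.05, a 20% difference. Not stated: power, sidedness, control mean and the unit of the SD. I assume hours and a two-sided test, with 80% power as the reference case.

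**1. Permitted dose range.** With one or two doses, the lowest total is 1 × 0.05 = 0.05 mg/kg (older band) and the highest is 2 × 0.1 = 0.20 mg/kg (younger band). The ratio is 0.20/0.05 = 4. The time from last dose to block is not limited.

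**2. The plan's own figure.** The total of 110 cannot be reproduced from the stated inputs, because power and control mean are missing. Solving back from 55 per arm:
- Difference = 2.5 × (1.960 + 0.842) × √(2/55) = 2.5 × 2.802 × 0.1907 = 1.34 h. If that is 20% of the control mean, the mean is 1.34/0.20 = 6.7 h.
- Two-sided with 90% power, the same formula gives 1.55 h and 7.7 h. One-sided with 80% power, it gives 1.19 h and 5.9 h.

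A control mean of about 6 to 8 h is therefore the plausible range.

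**3. Bias and type I error.** In 20,000 simulated trials of 55 per arm, half of all patients, regardless of arm, had their time lengthened by 1, 2 or 4 h. The mean between-arm bias was about 0 and the type I error about 5% in each case. Power fell from about 79% with no shift to 77% at 1 h and 73% at 2 h. The 4 h case gave 59%, but it adds a whole dosing interval to half the patients and nothing to the rest. I use it only as a stress test of the error rate.

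**4. Lower end: morphine and block wear off in parallel.** Let rescue occur when the later of the two ends: T = max(B, M). Here B is normal with mean 5.9, 6.7 or 7.7 h and SD 2.5 h, and M (morphine cover remaining after the block) is uniform over 0–2 h or 0–4 h. Simulation gives:
- M outlasts B in between under 1% and about 8% of patients.
- The mean delay is at most about 0.1 h.
- M explains at most about 0.13% of the variance of T.

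**5. Upper end: residual morphine simply adds to block duration.** Let T = B + M, with M uniform over width w and variance w²/12.
- w = 2: variance 4/12 = 0.33 h², SD 0.58 h. w = 4: variance 16/12 = 1.33 h², SD 1.15 h.
- 95% chance shift between arms, 1.96 × SD × √(2/55): 1.96 × 0.58 × 0.1907 = 0.22 h and 1.96 × 1.15 × 0.1907 = 0.43 h. Against 1.34 h these are 16% and 32%.
- For scale, the standard error of the whole difference is 2.5 × 0.1907 = 0.48 h, so its 95% half-width is 1.96 × 0.48, about 0.93 h.
- If this variance comes on top of the planning SD, the total SD is √(6.25 + 0.33) = 2.57 or √(6.25 + 1.33) = 2.75. Power is Φ(1.34/(2.57 × 0.1907) − 1.96) = 78% or Φ(1.34/(2.75 × 0.1907) − 1.96) = 72%, against 80% planned.
- If the SD of 2.5 already contains it, planned power is unchanged and the chance shift is already inside the 0.48 h.

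Steps 2 to 5 use normal theory for a mean time. They show order of magnitude only and do not predict the behaviour of a Cox model with censoring at 24 h or surgery.

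**The case against.** The strongest reply is that pre-block morphine will usually have gone by the time the block fails. Design spaces doses four hours apart. Background cites relief from this block lasting to 8 h. The sample size implies a control mean of about 6 to 8 h. Blocks that fail at 30 minutes, where residual morphine would matter most, are excluded. A block given on top of opioid is also a legitimate pragmatic question, since Background describes the block as an adjunct to oral analgesia that includes opioids. All of this stands, and it is why the lower end of the range is negligible. It does not remove the case for recording: the parallel model is itself an assumption, and without dose and time it cannot be checked.

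A reader might infer more than the documents support:
- **That the comparison is biased.** It is not. Pre-block doses precede the study injection, allocation is random and the trial is double-blind, so carry-over is balanced in expectation.
- **That adjustment would save a calculable share of patients.** Turning the additive variance share into a sample-size gain needs the additive assumption and a linear-model formula. The planned model is a Cox regression of a censored time, to which that formula does not apply.
- **That the exclusion must be widened to all opioids.** The rule is indeed silent on opioid given before hospital, although the Introduction says "Analgesia is a key component in the pre-hospital, preoperative and post-operative time periods for the hip fracture patient". But a broader dose count would still ignore timing, and it could make patients ineligible once they receive the protocol's own morphine. The documents give no pre-hospital opioid rates from which to judge the loss.
- **That the pain-score baseline must change.** The plan does not define it, but a sensible analyst would choose a pre-injection reading. The primary outcome does not depend on it.

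**Conclusion.** The concern holds as a matter of precision and chance imbalance only. The text establishes that pre-block morphine may vary four-fold per kilogram, that its timing relative to the block is neither limited nor listed for recording, that the same drug defines the primary event, and that no adjustment is named. The documents do not establish how much this matters.

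On the stated assumptions (SD in hours, two-sided test, 80% power, residual cover of up to 2 to 4 h), the effect runs from negligible under parallel wear-off to a modest loss of power if residual morphine adds fully to block duration and the planning SD does not already include it. Validity of the primary test is not in question. This is an optional improvement, worth making because it costs little.

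**What to change.** 1. On the data collection form, add the number and total mg/kg of opioid doses given before the block, including any pre-hospital dose, and the clock time of the last one.
2. In Data Analysis, pre-specify total pre-block dose, time from last dose to block, and age as covariates in the Cox model for the primary outcome. The plan does not tie its listed methods to outcomes, so the sentence should also say that this model is the primary analysis. The resulting hazard ratio is conditional on the covariates and should be reported as such.
3. While editing, reconcile the statement that every patient receives morphine with the as-needed wording. The two age bands also need reconciling, because a patient aged exactly 65 falls in neither. The definition of the dose covariate depends on both.

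The cost is a few extra data fields and three extra model terms. Treatment, eligibility and sample size do not change.

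### The treatment arm's bupivacaine maximum is printed as 175 kg, which is not a dose; the plan's own figures point to 175 mg, and the control arm should state the same rule

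*Combined protocol and SAP*

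**What the plan says.** In the combined protocol and SAP, under Design, the treatment group receives "Bupivacaine (0.5% or 5 mg/ml) 2.5 mg/kg (max dose 175 kg) + Ketamine (50 mg/ml) 2 mg/kg". The injectate volume is fixed: "Each patient will be given a volume of 40 mL - this will be a mixture of Bupivacaine, Ketamine and 0.9% NS", with saline filling whatever the drugs leave.

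The control group "will receive an ultrasound guided regional nerve block with Bupivacaine 0.5% only", and "this will be a mixture of Bupivacaine and 0.9% NS to make up the full volume of 40 mL". This bullet gives no mg/kg dose, no maximum, no split between drug and saline, and no reference back to the treatment group's dose.

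The Exclusion Criteria remove patients of 100 kg or more. The stated aim (Significance) is to "evaluate the effect of ketamine added to bupivacaine", and the Hypothesis begins "The administration of ketamine as an adjunct to bupivacaine". No other section gives a bupivacaine maximum in milligrams.

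**The concern.** The bracketed maximum is the only stated ceiling on the local anaesthetic dose, and its unit is a body weight. It cannot be applied literally as a drug limit. Taken as a weight limit of 175 kg it has no effect, because nobody at or near that weight is eligible.

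The cap matters in practice. At 2.5 mg/kg a working maximum of 175 mg would govern every eligible patient above 70 kg. Without it, the weight-based doses soon exceed the fixed syringe volume, so part of the eligible population has no recipe that satisfies every stated figure. The same section holds lipid emulsion ready as an antidote for severe side effects, so the dose limit should be legible without interpretation.

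The control-arm bullet is a secondary matter. The comparison isolates ketamine only if both arms receive bupivacaine by the same rule, and the text leaves that rule to be inferred.

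**Working it through.** **Inputs**

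- Bupivacaine 2.5 mg/kg at 5 mg/mL, which is 2.5/5 = 0.50 mL/kg (Design, treatment group).
- Ketamine 2 mg/kg at 50 mg/mL, which is 2/50 = 0.04 mL/kg (same place).
- Total volume 40 mL in each arm (Design).
- Eligible weight below 100 kg (Exclusion Criteria).

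**Step 1: the printed figure.** As a dose, 175 kg has no meaning. As a weight, 175 kg exceeds the 100 kg eligibility limit, so it never binds.

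**Step 2: the figure read as milligrams.** 175 mg ÷ 2.5 mg/kg = 70 kg, so the cap binds above 70 kg. 175 mg ÷ 5 mg/mL = 35 mL of bupivacaine.

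**Step 3: does 175 mg fit 40 mL?** Drug volume = min(0.50 × weight, 35) + 0.04 × weight. The weights below are illustrative.

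| Weight (kg) | Ketamine (mL) | Total drug, 175 mg cap (mL) | Total drug, no cap (mL) |
|---|---|---|---|
| 60 | 2.40 | 32.40 | 32.40 |
| 70 | 2.80 | 37.80 | 37.80 |
| 80 | 3.20 | 38.20 | 43.20 |
| 90 | 3.60 | 38.60 | 48.60 |
| 99 | 3.96 | 38.96 | 53.46 |

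With the cap, the mixture fits at every eligible weight. Saline is 2.2 mL at 70 kg and about 1.0 mL at 99 kg.

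**Step 4: is 175 mg the only cap that fits?** No. The largest fixed cap that fits up to 100 kg is (40 − 0.04 × 100) × 5 = 180 mg. The volume check is therefore consistent with 175 mg but does not single it out. The printed digits and the 70 kg multiple do that.

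**Step 5: what if the cap is ignored in the treatment arm?** Drug volume is 0.54 mL/kg and reaches 40 mL at 40/0.54 = 74.07 kg. Bupivacaine at that weight is 2.5 × 74.07 = 185.2 mg, and 185.2/175 = 1.058, about 6% over. Above that weight the stated doses no longer fit together. With full ketamine kept, the space left holds (40 − 0.04 × weight) × 5 mg of bupivacaine: 184 mg at 80 kg and 180.2 mg at 99 kg. The peak that fits is therefore about 185 mg. Below 70 kg the cap changes nothing.

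**Step 6: the control arm as worded.** 40 mL of undiluted 0.5% would hold 40 × 5 = 200 mg, and 200/175 = 1.143. The bullet requires some saline, so 200 mg is a strict upper bound that is never reached. Under the natural reading (2.5 mg/kg, maximum 175 mg), a control patient of 70 kg or more receives 35 mL of bupivacaine plus 5 mL of saline, the same 175 mg as in the treatment arm.

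**The case against.** The best reply is that the slip corrects itself. A maximum dose in kilograms is impossible, the figure directly follows a mg/kg dose, and 175 is 2.5 × 70. No rival reading is plausible, and the fixed volume limits the consequence of ignoring the cap. Most of this stands: 175 mg is the only plausible reading, and the treatment-arm excess that fits in 40 mL is about 6%. The documents do not describe how syringes are prepared, so one cannot say that staff would have only this text to work from.

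A reader might be tempted by three stronger claims, and the documents do not support them.

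- *That overflow above 74.1 kg proves the intended cap.* The words for a maximum dose show that a cap was intended. Overflow shows only that some cap is needed, and anything up to 180 mg would fit.
- *That the control arm may receive 200 mg, 14% above 175 mg.* The control injectate must contain saline, so 200 mg is not attained. The word only, set against bupivacaine plus ketamine in the preceding bullet, naturally means without ketamine. The Significance and Hypothesis sections both treat ketamine as an addition to the same bupivacaine.
- *That the arms will differ in bupivacaine and bias the comparison.* Under the natural reading there is no difference.

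The reply does not remove the point. An obvious intention is not a written limit, and this figure is an operative dosing instruction.

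**Conclusion.** The point holds as a safety-relevant error in a dosing instruction. The only stated bupivacaine maximum is in a unit that cannot limit a dose, and as a body weight it has no effect. The intended figure is almost certainly 175 mg. This is an inference from the digits and the 70 kg multiple, supported by the volume check, and it needs clinical confirmation.

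The size is modest. If the cap were ignored with full ketamine kept, bupivacaine in a 40 mL treatment syringe would reach at most about 185 mg, 6% above 175 mg, and the recipe could not be followed in full from 74.1 kg to the 100 kg limit. These figures assume the printed concentrations and the 40 mL total.

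The control-arm gap is missing detail with a clear natural reading and does not amount to a competing dose rule. It is worth closing in the same edit. Neither part predicts a bias or alters the sample size or the analysis.

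**What to change.** In the treatment-group bullet, change the unit so that the maximum reads 175 mg, after the clinical lead confirms that figure. In the control-group bullet, state the rule in full: bupivacaine 0.5%, 2.5 mg/kg, maximum 175 mg, with 0.9% saline to 40 mL. Ketamine is then the only written difference between the arms.

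The cost is one corrected unit, one added sentence, and a check that any preparation sheet matches.
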